17.3 Deaths, Serious and Other Significant Adverse Events

The number of deaths will be summarized in a table including all deaths, deaths in 30 days after last IMP administration, deaths in 100 days after last IMP administration and deaths after 100 days after last IMP administration, with a subgroup how many subjects died after last study date. The primary cause of death will be included in the listing.

Serious TEAEs, related serious TEAEs, serious TEAEs leading to permanent discontinuation of the trial treatment, serious AEs during follow-up period, fatal TEAEs and related fatal TEAEs will be summarized grouped by preferred term (order by decreasing frequency and by SOC or type, PT and highest NCI-CTCAE grade (order by decreasing frequency of SOC or type and by decreasing frequency of PT within SOC) as indicated:

- Serious TEAEs by PT
- Serious TEAEs related to enapotamab vedotin by PT
- Serious TEAEs leading to permanent discontinuation of the trial treatment by PT
- Serious TEAEs by SOC and PT and highest NCI-CTCAE grade
- Serious TEAEs related to enapotamab vedotin by SOC and PT and highest NCI-CTCAE grade
- Serious AEs during follow-up period by SOC and PT and highest NCI-CTCAE grade
- Fatal TEAEs by PT
- Fatal TEAEs related to enapotamab vedotin by PT

In addition, listings of serious AEs, fatal AEs and NCI-CTCAE grade \geq 3 AEs will be provided, similarly to the listing of all AEs.

Adverse events related to the trial treatment and serious adverse events reported during the follow-up period will be presented by SOC and PT and highest NCI-CTCAE grade.

17.4 Subject Diary

The information from the subject diaries will be listed and summarized.

Number of subjects completing the diary overall and whether they have taken the prophylactic laxatives or not will be presented.

A table will be included presenting what was prescribed as prophylactic therapy based on the diary data.

TPL N°: eTPL SA-02-01 TPL Version: 02 Of SOP SA-02.08

TPL Effective Date: 31 Mar 2016

Approved in Vault: 6/30/2021

17.5 Clinical Laboratory Data

The following laboratory parameters are measured:

- Biochemistry parameters: Sodium, potassium, magnesium, creatinine, calcium, blood urea nitrogen, AST, ALT, alkaline phosphatase, albumin, glucose, total bilirubin, lactate dehydrogenase, uric acid, C-reactive protein, lipase, amylase, gamma-glutamyl transferase, glycosylated hemoglobin, chloride, cholesterol, triglycerides, high-density lipoprotein and low density lipoprotein (calculated), thyroid stimulating hormone (TSH), triiodothyronine (T3) and thyroxine (T4)
- Hematology parameters: Red blood cell count, hemoglobin, hematocrit, mean corpuscular volume, mean corpuscular hemoglobin, mean corpuscular hemoglobin concentration, white blood cell count with differential, platelet count and reticulocyte count
- Coagulation factors (prothrombin time, international normalized ratio and activated partial thromboplastin time).

Safety laboratory assessments (biochemistry, hematology and coagulation factors) will be graded using NCI-CTCAE version 4.03 if possible. All laboratory assessments will be converted to the corresponding international system of unit. If the values are within the normal ranges (for both local and central laboratory data), the grading will be overwritten by grade 0.

For uric acid, grade 1 and grade 3 are defined with overlapping boundaries: >ULN - 10 mg/dl (590 µmol/L); for grade 1 without physiologic consequences and for grade 3 with physiologic consequences (no grade 2). In all listings and tables (e.g. shift-tables based on NCI-CTCAE-grade) where uric acid is presented with NCI-CTCAE grade: a footnote will be added:

"A uric acid value >ULN-590 μ mol/L is either NCI-CTCAE grade 1 if there is no physiological consequence or grade 3 if there is. In the absence of physiological consequence information and for the purpose of presentation in this listing/table/graph, such values are here considered to be grade 1".

Central laboratory results will be presented in shift tables and listed. Local laboratory results will be listed only.

Shift tables will be produced for all laboratory parameters graded by NCI-CTCAE grading. These tables will summarize the number of subjects with each baseline NCI-CTCAE grade and changes to the maximum NCI-CTCAE grade. For the calculation of the maximum NCI-CTCAE grade, both scheduled and unscheduled values available during the treatment period will be used.

For laboratory parameters that are not graded, shift tables based on normal ranges (low, high, normal) will be produced. These tables will summarize the number of subjects going from Normal/Low at baseline to High at any post-baseline, and going from Normal/High at baseline to Low at any post-baseline. Both scheduled and unscheduled values available during the treatment period will be used.

The number of subjects with at least one NCI-CTCAE grade 3 or grade 4 laboratory value during the treatment period will be summarized in a table overall and by laboratory parameter.

The following subject data listings will be produced for all laboratory parameters where NCI-CTCAE grades are defined:

• Listing of all laboratory abnormalities of NCI-CTCAE grade 3 or 4.

Page 33 of 46

TPL N°: eTPL SA-02-01 Of SOP SA-02.08 TPL Effective Date: 31 Mar 2016

• Listing of all laboratory data including NCI-CTCAE grades (if applicable) as well as classifications relative to the laboratory reference ranges separated by central and local laboratory results.

All other laboratory parameters will be listed by subject, laboratory parameter and visit in the above second set of listings with grades left empty. Values outside the laboratory reference range will be flagged.

In addition, the frequency of subjects with incidence of drug induced liver laboratory abnormalities will be summarized descriptively and listed. Drug induced liver laboratory abnormalities will be defined as subjects meeting or exceeding one of the following predefined limits post-baseline:

- AST and/or ALT > 3xULN
- AST and/or ALT > 5xULN
- AST and/or ALT > 10xULN
- AST and/or ALT > 20xULN
- AST and/or ALT > 3xULN and Total Bilirubin > 2xULN;
- AST and/or ALT > 3xULN and Total Bilirubin > 2xULN and ALP < 1.5xULN.
- AST and/or ALT > 3xULN and INR > 1.5

Of note, total bilirubin, ALP and/or INR measurements concurrent or within 30 days subsequent to ALT/AST elevation will be included for the assessment of the incidence.

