### **8.5.2 Hematology**

Blood samples will be drawn as according to [Table 9](#), [Table 10](#) and [Table 11](#).

The following hematology parameters will be analyzed centrally, as well as locally at site (the day before or on the day of each enapotamab vedotin administration):

Red blood cell count, hemoglobin, hematocrit, mean corpuscular volume, mean corpuscular hemoglobin, mean corpuscular hemoglobin concentration, white blood cell count with differential, platelet count, reticulocyte count and coagulation factors (prothrombin time, international normalized ratio and activated partial thromboplastin time).

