4.1 Trial Period and Visit Window Definitions

4.1.1 Trial Periods

Screening period will be defined as the period before the date of first investigational medicinal product (IMP) administration (enapotamab vedotin).

Treatment period including safety follow-up period will be defined as the period between the date of first IMP administration and the date of last IMP administration + 30 days or the end of treatment visit whichever comes later.

Follow-up period will be defined as the period between the end of treatment period including safety follow-up period + 1 day and the date of last contact.

TPL N°: eTPL SA-02-01 TPL Version: 02 Of SOP SA-02.08

Of SOP SA-02.08
TPL Effective Date: 31 Mar 2016
Approved in Vault: 6/30/2021

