4.6 Calculated Variables

The following general definitions will be used throughout the trial:

 Baseline is defined as the latest recorded measurement made before the first IMP administration (trial day 1). Measurements done on the same date as the first IMP administration will be considered as done before the first IMP administration unless specified otherwise. For PK variables, the first IMP administration will be time 0.

TPL N°: eTPL SA-02-01 TPL Version: 02

Of SOP SA-02.08
TPL Effective Date: 31 Mar 2016
Approved in Vault: 6/30/2021

- Change from baseline is defined as the post-baseline value baseline value. Change from baseline will be missing when either post-baseline or baseline value is missing.
- Percent change from baseline is defined as 100*(post-baseline value baseline value)/baseline value. If the baseline value is 0 and the post-baseline value is 0, the change from baseline and the percent change from baseline are both 0. If the baseline value is 0 and the post-baseline value is not 0, the change from baseline is the same as the post-baseline value and the percent change from baseline will be undefined (missing).

The following variables will also be computed for the analyses described later on:

- Time (in months) from initial diagnosis of primary site to start date of IMP: (date of first IMP administration date of first diagnosis)/30.4375.
- Time (in months) since most recent recurrence/relapse or progression to start date of IMP: (date of first IMP administration – date of most recent recurrence/relapse or progression)/30.4375.
- Time (in months) since (last) biopsy to start date of IMP: (date of first IMP administration date of (most recent) biopsy before or on the start date of IMP)/30.4375. Time since biopsy will be included in the listing, time since last biopsy will be included in the biopsy table (only one result per subject).
- Time (in months) since biopsy to start date of IMP for post-baseline biopsy data: (date of (most recent) biopsy date of first IMP administration +1)/30.4375.
- Time (in months) since most recent recurrence/relapse or progression to date of most recent biopsy: (date of most recent biopsy date of most recent recurrence/relapse or progression)/30.4375.
- Time (in months) between fresh biopsy and archival biopsy (when both are available): (date of fresh biopsy date of archival biopsy)/30.4375 (only listed).
- Duration of exposure (days): (end date of IMP date of first IMP administration + 1),

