17.6 Other Safety Data

17.6.1 Vital Signs

Vital signs results will be listed with a flag marking the clinically notable values for each of the following parameters:

Clinically notable elevated values

- Systolic BP: >=180 mmHg and an increase >=20 mmHg from baseline
- Diastolic BP: >=105 mmHg and an increase >=15 mmHg from baseline.
- Weight: Increase from baseline of 10%
- Heart rate: >=120 bpm with increase from baseline of >=15 bpm
- Temperature: >38 °C

Clinically notable below normal values

- Systolic BP: <=90 mmHg and a decrease >=20 mmHg from baseline
- Diastolic BP: <=50 mmHg and a decrease >=15 mmHg from baseline
- Weight: decrease from baseline of >=10%
- Heart rate: <=50 bpm with decrease from baseline of >=15 bpm
- Temperature: <35 °C

The number of subjects with at least one clinically notable value as defined above will be summarized in a table.

F

TPL N°: eTPL SA-02-01 TPL Version: 02 Of SOP SA-02.08

OF SOP SA-02.08

TPL Effective Date: 31 Mar 2016

Approved in Vault: 6/30/2021

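### The Grade 3/4 laboratory count (Table 14.03.19) is taken over a treatment period that includes the Cycle 1 Day 1 baseline sample, so a pre-dose abnormality can be counted as a treatment-period one

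*SAP*

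**What the plan says.** Four parts of the SAP meet here.

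- **Trial periods (SAP 4.1.1).** Screening "will be defined as the period before the date of first investigational medicinal product (IMP) administration". The treatment period is "the period between the date of first IMP administration and the date of last IMP administration + 30 days", or runs to the end of treatment visit if that is later. Both definitions work by calendar date; neither uses a time of day.
- **Baseline (SAP 4.6).** "Baseline is defined as the latest recorded measurement made before the first IMP administration (trial day 1"). The next sentence adds: "Measurements done on the same date as the first IMP administration will be considered as done before the first IMP administration unless specified otherwise".
- **Grade 3/4 count (SAP 17.5).** "The number of subjects with at least one NCI-CTCAE grade 3 or grade 4 laboratory value during the treatment period will be summarized", overall and by parameter. The output is Table 14.03.19, whose title mentions only Grade 3/4 laboratory results.
- **Graded shift tables (SAP 17.5).** For the maximum grade, "both scheduled and unscheduled values available during the treatment period will be used". The titles of these tables (14.03.13, 14.03.15 and 14.03.17) refer to the highest post-baseline grade, and protocol 10.3.7 compares baseline with the worst post-baseline value.

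Two other outputs in SAP 17.5, the normal-range shifts and the liver abnormality table, are limited to post-baseline values in the text itself.

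**The concern.** The first-dose date is outside screening and so inside the treatment period. A laboratory sample of that date is also, by rule, pre-dose. One Day 1 record can therefore be the subject's baseline and at the same time a value of the treatment period.

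For the Grade 3/4 count this matters directly. A severe value that was present before any drug was given, and that never recurs, puts the subject into a table that will be read as abnormalities arising on treatment. Safety laboratory parameters are a secondary endpoint, and the trial has no control arm that would show the background rate.

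**Working it through.** The plan states no figure on this point, so there is none to reproduce. The check applies the rules to a test subject and then shows how the size depends on assumed rates.

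**Is the Day 1 sample really there?** Protocol Tables 9, 10 and 11 schedule hematology and biochemistry at Cycle 1 Visit 1 in both escalation arms and in the expansion part. Protocol 8.5 has those samples tested centrally. Hematology, for example, is "analyzed centrally, as well as locally at site (the day before or on the day of each enapotamab vedotin administration"); the day-before option belongs to the local sample, and SAP 17.5 only lists local results. The central sample that feeds the tables is therefore scheduled for the first-dose date.

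**Does the treatment period include that date?** If the word between in 4.1.1 were read as excluding its endpoints, the first-dose date would belong to no period at all. SAP 4.7 also imputes certain missing adverse event start dates to the first-dose date in order to assign the treatment-emergent flag, which presupposes that the date is in the period.

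**Test subject, one parameter:**

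| Record | Grade | SAP 4.1.1 period | SAP 4.6 status |
|---|---|---|---|
| Screening | 3 | Screening | Pre-dose |
| C1D1 | 3 | Treatment | Pre-dose; baseline |
| C1D8 | 1 | Treatment | Post-baseline |
| C2D1 | 2 | Treatment | Post-baseline |

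- SAP 17.5 as written: maximum over the treatment period = max(3, 1, 2) = 3. The subject is counted in Table 14.03.19.
- Post-baseline values only: max(1, 2) = 2. The subject is not counted.

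The screening value plays no part in either result. Only first-dose-date records are affected.

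**Which parameters are exposed?** The local recheck around C1D1 in protocol 8.5 covers GFR, ALT, AST, bilirubin, hemoglobin, neutrophils, platelets and, in melanoma, LDH. Cohort 7 also has an albumin limit. Electrolytes, glucose, lipase, amylase, GGT and lymphocytes are measured but have no general entry limit.

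**Illustrative size for one parameter.** Let *b* be the share of subjects with a Grade 3/4 value on Day 1, and *q* the share of those who also have one later and so are counted correctly either way. Then

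- expected extra subjects = N × b × (1 − q)
- chance of at least one = 1 − [1 − b(1 − q)]^N

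Both *b* and *q* are assumptions. The planned sizes N come from protocol Table 1.

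| N | b = 1%, q = 0.8 | b = 10%, q = 0.5 |
|---|---|---|
| 22 | 22 × 0.002 = 0.04 | 22 × 0.05 = 1.1 |
| 37 | 37 × 0.002 = 0.07 | 37 × 0.05 = 1.85 |
| 82 | 82 × 0.002 = 0.16 | 82 × 0.05 = 4.1 |
| 349 | 349 × 0.002 = 0.7 | 349 × 0.05 = 17.5 |

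At N = 37 the chance of at least one extra subject runs from 1 − 0.998^37 = 7% to 1 − 0.95^37 = 85%.

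**The case against.** The best reply is that SAP 4.6 sets general definitions for the whole trial. A programmer who applies its same-date rule, and sees that neighboring outputs are post-baseline, might drop the Day 1 record without being told to. That is possible, but the text does not require it: the sentence for Table 14.03.19 names only the treatment period, and its title adds no limit. That the limit is written out for the normal-range shifts and the liver table makes its absence here more noticeable.

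It can also be said that the table is descriptive, with no test or dose decision attached, that adverse events are handled separately, and that the Grade 3/4 listing and the baseline grades in the shift tables let a careful reader find pre-existing abnormalities. This is fair and limits the importance of the point. Investigators also review a broad local panel before each dose, which may make severe Day 1 values rarer.

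A reader might infer more than the documents support:

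- **That every worst-grade rule in 17.5 is affected.** The normal-range shifts and the liver table already say post-baseline.
- **That the graded shift tables can never show improvement.** This would follow from the body sentence alone, for subjects with a Day 1 baseline. The table titles and protocol 10.3.7 say otherwise, and SAP 4.9 lists no departure from the protocol on this rule. It is a wording conflict, not an established miscount.
- **That a screening fever enters the vital-signs table.** SAP 17.6.1 says only "The number of subjects with at least one clinically notable value as defined above will be summarized in a table", without naming a period. Silence does not settle what is included, and only temperature is open, since the other limits require a change from baseline.
- **That uric acid is a clear example.** SAP 17.5 sets values between the ULN and 590 µmol/L to Grade 1.

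**Conclusion.** The point holds for Table 14.03.19. Read literally, SAP 4.1.1, 4.6 and 17.5 count a subject whose only Grade 3/4 value is the Day 1 baseline sample, and nothing in the protocol or SAP removes that record. For the graded shift tables there is a conflict between the body text and the titles that should be cleared up. The other laboratory summaries named above are sound.

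The size cannot be settled from the documents. The ranges above rest on assumed rates and planned maximum enrolment, and apply to one parameter at a time. They should not be read as an estimate for the overall row: there, a false addition requires that the subject has no later Grade 3/4 value in any graded parameter, so masking is more likely. The direction is known: the count can only be too high. It is a modest defect in a secondary safety output, and easy to correct.

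**What to change.** 1. In SAP 17.5, restrict the Grade 3/4 count to post-baseline values up to the end of the treatment period. In the program, select records dated after the first-dose date. Removing only the record flagged as baseline could leave a second sample of the same date, which SAP 4.6 also treats as pre-dose.
2. In the graded shift-table paragraph, insert the same post-baseline limit so that it agrees with the table titles and protocol 10.3.7.
3. Leave the normal-range shift and liver table text unchanged.
4. The SAP addendum (section 2.1) states that data to 22 March 2021 have already been reported. So check the filter actually used for Tables 14.03.19, 14.03.13, 14.03.15 and 14.03.17, and correct or footnote the output if baseline records were included.

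The cost is a phrase in two sentences and a check of one program filter. Grade 3/4 counts may become slightly lower. An unscheduled sample drawn after the infusion on Day 1 would also be left out, although SAP 4.6 already treats it as pre-dose.

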4. Age  $\geq 18$  years.
5. Have an acceptable renal function defined as:
- Glomerular filtration rate (GFR)  $\geq 40$  mL/min/1.73 m^2 – e.g., according to the abbreviated Modification of Diet in Renal Disease (MDRD) equation:  

$$\text{GFR} = 186 \times (\text{SCr}^{-1.154}) \times (\text{age}^{-0.203})$$
 (where SCr, the serum creatinine level, is expressed in mg/dL; multiply it by 0.742 if the patient is female; multiply it by 1.212, if the patient is African-American).
  - Not being on dialysis

Document Name: GCT1021-01 Protocol

Document Number: TMF-03326

Version: 11.0

---

6. Have an acceptable liver function defined as:
  - Alanine aminotransferase (ALT) and aspartate aminotransferase (AST)  $\leq 3$  times the ULN; if liver tumor/ metastases are present, then  $\leq 5 \times$  ULN is allowed.
  - Bilirubin  $\leq 1.5 \times$  ULN, except in patients diagnosed with Gilbert's syndrome, direct bilirubin  $\leq 2 \times$  ULN
7. Have an acceptable hematological status defined as:
  - Hemoglobin  $\geq 5.6$  mmol/L ( $\sim 9$  g/dL).
  - Absolute neutrophil count (ANC)  $\geq 1500/\mu\text{L}$  ( $1.5 \times 10^9/\text{L}$ ).
  - Platelet count  $\geq 100 \times 10^9/\text{L}$ .
8. Have an Eastern Cooperative Oncology Group (ECOG) performance status of 0 or 1.
9. Life expectancy of at least 3 months.
10. Patients, both females and males, of childbearing/reproductive potential must agree to use adequate contraception while included in the trial and for 6 months after the last infusion of enapotamab vedotin (see [Appendix V](#)).
11. Patients must provide signed ICF.

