Table 14.03.12: Subject Diary Data including Prophylactic Laxatives	X	X
Table 14.03.13.xx: Biochemistry Laboratory Results - Shift Table from Baseline NCI-CTCAE Grade to Highest Post-Baseline NCI-CTCAE Grade	X	X
Table 14.03.14.xx: Biochemistry Laboratory Results - Shift table from Baseline to Maximum/Minimum Post-Baseline Abnormality	Х	Х
Table 14.03.15.xx: Hematology Laboratory Results - Shift Table from Baseline NCI-CTCAE Grade to Highest Post-Baseline NCI-CTCAE Grade	Х	Х
Table 14.03.16.xx: Hematology Laboratory Results - Shift table from Baseline to Maximum/Minimum Post-Baseline Abnormality	Х	Х
Table 14.03.17.xx: Coagulation factors Laboratory Results - Shift Table from Baseline NCI-CTCAE Grade to Highest Post-Baseline NCI-CTCAE Grade	Х	X
Table 14.03.18.xx: Coagulation factors Laboratory Results - Shift table from Baseline to Maximum/Minimum Post-Baseline Abnormality	Х	X
Table 14.03.19: NCI-CTCAE Grade 3/4 Laboratory Results	X	X
Table 14.03.20: Subject Incidence of Drug Induced Liver Laboratory Abnormalities	Х	X
Table 14.03.21: Vital Signs Abnormalities	X	X
Table 14.03.22: Body Weight over Time - Descriptive Statistics	Х	X
Table 14.03.23.01: ECG Measurements over Time – Descriptive Statistics	Х	X
Table 14.03.23.02: ECG Abnormalities over Time	Х	X
Table 14.03.24: ECOG Performance Score over Time	Х	X
Table 14.03.25: Pregnancy Test Results over Time	Х	X
Exploratory	Dose- Escalation Part	Expansion Part
Table 14.04.01.01.a:		
Table 14.04.01.01.b:		
Table 14.04.01.02.a:		
Table 14.04.01.02.b:		
Table 14.04.01.03.a:		
Table 14.04.01.03.b:		
Table 14.04.02.01: Table 14.04.02.02:		
Table 14.04.02.03:		

 $^{^{\}ast}$ Only most frequent AEs (> X% of Any Grade overall) will be included. The X% will be defined at the time of the analysis programming.

TPL N°: eTPL SA-02-01 TPL Version: 02

Of SOP SA-02.08
TPL Effective Date: 31 Mar 2016
Approved in Vault: 6/30/2021

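### The *drug induced* liver table ignores baseline, so patients with liver metastases who enter at >3 to 5xULN and do not change are counted in its lowest row

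*SAP*

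**What the plan says.** SAP Section 17.5 plans a summary and listing of liver laboratory abnormalities: "Drug induced liver laboratory abnormalities will be defined as subjects meeting or exceeding one of the following predefined limits post-baseline". Seven limits follow. Four concern transaminases alone (above 3, 5, 10 and 20xULN). Three combine "AST and/or ALT > 3xULN" with total bilirubin >2xULN, with total bilirubin >2xULN and ALP <1.5xULN, or with INR >1.5. The only further rule concerns timing: "total bilirubin, ALP and/or INR measurements concurrent or within 30 days subsequent to ALT/AST elevation will be included". The output is "Table 14.03.20: Subject Incidence of Drug Induced Liver Laboratory Abnormalities". SAP Addendum Section 3.8 repeats the definition for Table A.14.03.14.

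Protocol Section 6.1, inclusion criterion 6, sets the entry limits. ALT and AST may be up to 3xULN, but "if liver tumor/ metastases are present, then" up to 5xULN is accepted. Bilirubin may be up to 1.5xULN, "except in patients diagnosed with Gilbert's syndrome, direct bilirubin" up to 2xULN being the limit in that group. No inclusion or exclusion criterion limits INR.

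**The concern.** The title and definition attribute to the drug any value above a fixed limit after the first dose. The lowest limit lies inside the range that the protocol accepts at entry for patients with liver metastases. For those patients the first post-baseline sample can meet the definition with no change at all.

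Elsewhere the SAP usually takes baseline into account. Section 17.6.1 adds a change condition to its blood pressure limits, for systolic pressure "and an increase >=20 mmHg from baseline", and also conditions heart rate and weight on change. Section 17.6.3 shows the QT, PR and QRS categories at baseline as well as afterwards. Section 17.2 counts adverse events only if they started or worsened on treatment. The liver table does none of this.

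Establishing the safety profile is part of the primary objective (Protocol Section 4.1), and this is the only planned output that combines liver tests. A reader who takes its title literally would read abnormalities present at entry as liver toxicity.

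**Working it through.** The documents give no rate or target for this table, so there is no figure to reproduce. The check has two parts.

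**1. Which rows can be met by values that were allowed at entry and then stayed the same?**

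Inputs are the limits in criterion 6, the absence of an INR limit, and the strict inequalities in the SAP rows. Entry limits carry over to baseline because Protocol Sections 6 and 8.5 require eligibility to hold until the first dose.

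| Row | No liver metastases (ALT/AST ≤3x, bilirubin ≤1.5x) | Liver metastases (ALT/AST ≤5x, bilirubin ≤1.5x) | Liver metastases and Gilbert's (total bilirubin not capped) |
|---|---|---|---|
| >3x | no | **yes** | **yes** |
| >5x, >10x, >20x | no | no | no |
| >3x and bilirubin >2x (with or without the ALP condition) | no | no | **possible** |
| >3x and INR >1.5 | no | **yes**, if INR already >1.5 | **yes**, if INR already >1.5 |

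The Gilbert's cell needs four things in one patient: the syndrome, liver metastases, ALT/AST above 3xULN and total bilirubin already above 2xULN. It arises because the entry limit for that group is on direct bilirubin while the table uses total bilirubin.

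**2. How many patients could this be?**

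Let q be the share of patients whose ALT/AST is >3 to 5xULN at baseline and still above 3xULN at some later sample. The extra count in the >3xULN row is N × q. The documents do not give q, so every value below is an assumption. N is the planned maximum: 349 for the expansion part, 37 for a typical full cohort.

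- If q is set directly at 1%, 5% or 10%: 349 × 0.01 = 3.5; 349 × 0.05 = 17.5; 349 × 0.10 = 34.9. For a cohort of 37: 0.4, 1.9 and 3.7.
- If q is built from 20–40% with liver metastases and 2–10% of those entering above 3xULN: q = 0.20 × 0.02 = 0.4% up to 0.40 × 0.10 = 4%. That gives 349 × 0.004 = 1.4 up to 349 × 0.04 = 14.0.

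Effect on the displayed percentage, if a further assumed 5% of the other patients newly exceed 3xULN: displayed rate = (1 − q) × 5% + q.

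- q = 1%: 4.95% + 1% = 5.95%
- q = 5%: 4.75% + 5% = 9.75%
- q = 10%: 4.5% + 10% = 14.5%

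No comparable figure can be offered for the combined rows, because nothing in the documents bears on baseline INR or on the frequency of Gilbert's syndrome.

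**The case against.** The strongest reply is that the information is largely available elsewhere. The SAP 17.5 shift tables show baseline against worst grade: "These tables will summarize the number of subjects with each baseline NCI-CTCAE grade and changes to the maximum NCI-CTCAE grade". Protocol Table 8 places AST/ALT of >3 to 5xULN in Grade 2, so an unchanged patient would appear there as Grade 2 to Grade 2. The liver cases and all laboratory values are listed, liver metastases are tabulated at baseline (SAP Section 7), and relatedness is reported through the adverse event tables. Absolute limits are not unique to this table either: the Grade 3/4 laboratory table and the temperature limits also ignore baseline. Laboratory parameters are a secondary endpoint, and no test, dose decision or stopping rule uses the table. The addendum adds on-treatment data from only 3 subjects.

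Most of this stands, and it keeps the point small. Two parts do not answer it. The shift tables treat one analyte at a time and say nothing about the combined rows. They are also not repeated in the addendum: Table A.14.03.14 is its only laboratory table and covers all data from trial start (Addendum Section 3), while its listings hold only data after 22 March 2021 (Addendum Section 4.2).

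A reader might infer that the combined transaminase-and-bilirubin rows will fill with patients who were abnormal at entry. The documents do not support that, because bilirubin is capped at 1.5xULN at entry outside Gilbert's syndrome. A patient stable at 4xULN whose bilirubin then rises with liver progression does enter those rows, but through a real post-baseline change. That raises a question of attribution, which a screening table should leave open.

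**Conclusion.** The point holds in limited form. As written, the rule counts unchanged entry values as drug-induced in the >3xULN row for patients with liver metastases, and in the >3xULN-plus-INR row where INR was already above 1.5. The bilirubin rows are exposed only in the rare Gilbert's case, and the three higher transaminase rows not at all.

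The size is unknown. Across the assumptions tried it is about 1 to 35 of 349 patients in the >3xULN row, and roughly none to four in a cohort of 37. These figures assume full enrolment and that each such patient stays above 3xULN at some post-baseline sample. They do not show that the trial's liver toxicity is materially overstated. No inference, efficacy result or sample size depends on the table. This is a cheap improvement to how a descriptive safety output is labelled and read.

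**What to change.** In SAP Section 17.5 and Addendum Section 3.8, for Tables 14.03.20 and A.14.03.14:

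- Keep the present unconditional count in every row.
- Beside it, split each row by baseline ALT/AST (≤3xULN, >3xULN). For the combined rows also show baseline total bilirubin (≤2xULN, >2xULN) and baseline INR (≤1.5, >1.5) where available.
- Retitle both tables *liver laboratory abnormalities* and drop *drug induced* from the definition.

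Baseline is already defined in SAP Section 4.6, and transaminases, bilirubin and INR belong to the screening panels, so no new data are needed. If the outputs already exist, the split can be added as a column or footnote. The cost is one extra split with small cell counts.

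Subjects should not be removed from the combined rows because ALT/AST did not newly exceed its limit or worsen. A patient stable at 4xULN whose bilirubin newly rises above 2xULN would then vanish from the row meant to flag such cases. The same filter on the single rows would break their nesting: a patient going from 4x to 12xULN would appear under >10x but not under >3x.
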